Assessments	Pre-Intervention Assessment	1 week prior to STELLA-FTD start
STELLA-FTD Intervention	Meet with Faculty and Guest Speakers for 8 weekly, 1-hour, sessions	1 week after pre-intervention assessment
Assessment	Mid-intervention Assessment	4 weeks after start of STELLA-FTD sessions
Assessment	Post Assessment 1	Within one week of completion of STELLA-FTD
Assessment	Post-Assessment 2	2 months after end of STELLA-FTD
Assessment	Post-Assessment 3	6 months after end of STELLA-FTD
Weekly Orbit Surveys: Distributed weekly		
Orbit surveys start after enrollment and continue until all surveys are completed		

Measures (Table 3). The primary outcome variable, burden, will be assessed with the 24-item RMBPC (2), which measures the frequency of care recipient behavioral symptoms and care partner reactions to these behaviors. The RMBPC was chosen because it aligns with our theoretical foundation that assumes burden is a result of care partner reactions to behavioral symptoms. The RMBPC has been used in Teri's work (30) and our telehealth

studies, (29, 31, 33, 34) including the STELLA-FTD pilot, allowing for comparison across studies.

Self-efficacy, the mediating variable, will be assessed using Fortinsky's measurement of family care partner self-efficacy for managing dementia (3). We considered the other measures, but Fortinsky's assesses the targets in STELLA-FTD: behavior symptom management and service use.

We will measure care partner preparedness for current and future challenges (63) and personality type to test the effect of a group-based intervention (64).

For care partners in STELLA-FTD+ABC, we will assess the results of the care partners' personalized ABC plans prior to and after the 8-week intervention by collecting data on the frequency of their identified behaviors, and their reactions to them, on their Personalized Target Behavior Survey (29, 30). We will collect data on number of ABC plans each care partner writes on the Orbit weekly survey, weeks 4-36.

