STELLA-FTD contact ⁽²⁹⁾	STELLA-FTD Care Partner contact post intervention
Orbit Survey: Distributed weekly starting Week 5 ⁽²⁹⁾: # of ABC plans (ABC group), service use, burden	

We will implement the above measures using Qualtrics or REDCap Survey Platforms. The surveys will be sent to the Care Partners using these platforms. Auto-reminders will be sent to the Care Partners until they complete the surveys. If they do not complete the surveys within 5 working days, the STELLA-FTD coordinator may call them to identify barriers to completing the surveys. The electronic functionality allows Care Partners to complete surveys in the privacy of their homes, at a time that works for them. The Qualtrics and REDCap platforms are HIPAA compliant and secure. We will assess completion rates and internal consistency of the online platform surveys. Focus group participants will be queried about their experience with the platform.

7) Data and Specimens

a) Handling of Data and Specimens

No biological or genetic specimens will be collected in this study. Data from the measures described above will be collected via the secure Qualtrics or REDCap systems and then downloaded to a secure OHSU file for analyses. Video-recordings of focus groups and intervention sessions to be used for quality assurance and fidelity assessment. Videos not used for these tasks may be deleted. De-identified transcripts of qualitative data will also be downloaded to a secure OHSU file for analysis.

No biological or genetic specimens will be collected in this study. Data from the measures described above will be collected via the secure Qualtrics or REDCap systems and then downloaded to a secure OHSU file for analyses. Video-recordings of focus groups and intervention sessions to be used for quality assurance and fidelity assessment. Videos not used for these tasks may be deleted. De-identified transcripts of qualitative data will also be downloaded to a secure OHSU file for analysis.

b) Sharing of Results with Subjects

If the burden or depression scores indicate severe depression or burden, the Care Partner may be informed, at the discretion of the PI. The Care Partner may be referred to appropriate services if deemed necessary (e.g., social worker or other counseling services). The other results may be provided, if asked, after all data is collected, analyzed and published.

c) Data and Specimen Banking

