H3: Care partners with higher self-efficacy will have lower burden scores. In the second step to test for H3, we will construct a mixed effect model on the RMBPC ⁽²⁾ reactivity score as the outcome. Total self-efficacy score ⁽³⁾ will be included as a continuous independent variable; time will be included as a continuous variable. The interaction between total self-efficacy score and time (self-efficacy score x time) will also be included. Random intercepts will be incorporated for subject specificity in the model to account for clustering effect within subject over time. A hypothesis test for the coefficient of the interaction term (self-efficacy score x time) will be performed to assess the relationship between change on primary outcome (RMBPC reactivity score ⁽²⁾) and total self-efficacy score ⁽³⁾, over time.

H4: Self-efficacy will partially mediate the relationship between ABC training and burden. In the third step, a mixed effect model on RMBPC reactivity score ⁽²⁾ will be constructed based on the model in H1. We will extend the established model in H1 to include total self-efficacy score as a continuous covariate and the interaction term between total self-efficacy score and time (self-efficacy score x time) will also be included. We expect the interaction term coefficient (group x time) in model for H1 will be significant, and the coefficient of the interaction term between group and time (group x time) will be attenuated and may become non-significant after extending the model to add total self-efficacy score as a covariate and the interaction between total self-efficacy score and time (total self-efficacy score x time). This will indicate that the self-efficacy has a mediated effect on the association between the intervention and change in the primary outcome (RMBPC reactivity score ⁽²⁾) as compared to the control group. We will also extend these models to include diagnosis, frequency of behavioral symptoms as measured on the RMBPC ⁽²⁾, socio-demographic covariates and preparedness (78). All of results above will be considered significant at $\alpha = 0.05$, with two-sided tests.

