Items from the Orbit survey ⁽²⁹⁾ will be examined as repeated weekly measures in each group for an exploratory analysis. We will first explore the data descriptively and then manage or transfer the variables from survey items if needed. Categorical variables will be displayed as frequency (%) and continuous variables will be shown as mean (SD) or median (25th percentile, 75th percentile). These measures will be compared between two groups at each week using two-sample t test for continuous variables and chi-square test for categorical variables. Within each group, we also plan to evaluate the change of measure over time using line charts and compare the line pattern between two groups for continuous variables. The change in continuous variables between two time points within the group can be assessed using paired t-tests. The change in categorical variables between two time points within the group can be assessed using chi-square test.

Aim 3. Standardize materials and fidelity assessment processes.

Qualitative data from the focus groups will be analyzed using Thomas's inductive analytic approach ^(15, 65). We will create categories that will inform further revision of STELLA-FTD materials to be used in a future NIH Stage 2 study ⁽¹⁾.

9) Privacy, Confidentiality and Data Security

Standard institutional practices will be followed as described in the OHSU Information Security and Research Data Resource Guide to maintain the confidentiality and security of data collected in this study. Study staff will be trained with regard to these procedures.

All scales will be de-identified and a participant number will be assigned to each scale for data management. All data will be kept on the limited-access drives or computers at OHSU or in a locked location in the OHSU ADRC. Documents used for the intervention may be stored with the interventionist and RA in a secure location in the staff member's home. All documents will be shredded or returned to the OHSU ADRC at the completion of the intervention. These documents will not contain any PHI, but will contain the participant's study ID #.

Data for this project will be stored in OCTRI's installation of REDCap, a highly secure and robust web-based research data collection and management system.

The REDCap servers are housed behind both the OHSU firewall and a second ACC firewall. All web-based data transmissions are encrypted with industry-standard SSL methods.

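### The Orbit analysis pairs the within-group test for continuous items but names an unqualified chi-square test for categorical items, although the same care partners answer at both time points.

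*Combined protocol and SAP*

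**What the plan says.** Section 8 (Data Analysis), in the paragraph on the Orbit survey after H4, says that the items "will be examined as repeated weekly measures in each group for an exploratory analysis". Three test rules follow.

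- Between arms: "These measures will be compared between two groups at each week using two-sample t test for continuous variables and chi-square test for categorical variables".
- Within an arm, continuous items: "The change in continuous variables between two time points within the group can be assessed using paired t-tests".
- Within an arm, categorical items: "The change in categorical variables between two time points within the group can be assessed using chi-square test".

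The paragraph names no paired test for categorical data, no longitudinal model for these items and no significance level. The nearest level is in the preceding H4 paragraph, "All of results above will be considered significant at $\alpha = 0.05$, with two-sided tests", which looks back to the Aim 2 hypotheses.

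The number of weekly surveys is given in three ways. Section 6, Measures, says "We will collect data on number of ABC plans each care partner writes on the Orbit weekly survey, weeks 4-36". The last row of Table 3 says "Orbit Survey: Distributed weekly starting Week 5". Table 2 has the surveys begin once a care partner is enrolled.

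**The concern.** Two answers from one care partner are not independent. The plan allows for this for continuous items and then, in the next sentence, names for categorical items the same unqualified test that it uses for two separate randomised arms. Taken literally, there are two ways to run it, and neither tests change properly.

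1. Tabulate time point by response and treat the two rows as different people. The standard error then ignores the within-person covariance. With positive correlation it is too large, and real change may be missed.
2. Cross-tabulate the first answer against the second. The test then asks whether the answers are related. Stable answers give a very small p-value, which could be reported as significant change.

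The second is the more damaging, because it can turn no change into a positive finding. What is at stake is the interpretation of whichever Orbit items prove to be categorical, in a Stage 1B trial that is meant to prepare a Stage 2 study.

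A separate and lesser matter is that the arms are tested afresh every week, with nothing said about how the resulting series of p-values will be read.

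**Working it through.** **Inputs from the documents.** 117 to 128 per group, effect size 0.3, three measurements, ICC 0.5 to 0.6, alpha 0.05, 80% power (section 4, sample size calculation).

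**Assumptions.** The documents give no prevalence, size of change or within-person correlation for any Orbit item. I take a prevalence of 30%, a fall to 20%, and phi from 0.1 to 0.5. The 128 pairs are borrowed from the primary-outcome calculation. Tests are at an assumed 0.05.

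**Step 1. Reproduce the plan's own figure.** n per group = 2(1.960 + 0.842)² × [1 + (3 − 1) × ICC] / (3 × 0.3²). ICC 0.5 gives 116.3, rounded up to 117. ICC 0.6 gives 127.9, rounded up to 128. Both match, so 128 is a fair planning number of pairs.

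**Step 2. Reading 1, no change.** The true variance of the difference is (1 − phi) times the variance that the unpaired test assumes. Its type I error is therefore 2[1 − Φ(1.96/√(1 − phi))].

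- phi 0.1: 1.96/0.949 = 2.07, giving 3.9%
- phi 0.3: 1.96/0.837 = 2.34, giving 1.9%
- phi 0.5: 1.96/0.707 = 2.77, giving 0.6%

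Simulation agrees with these figures, and McNemar's test (uncorrected) stays near 5% throughout.

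**Step 3. Reading 1, a fall from 30% to 20%.** At phi 0.5 the expected counts in 128 pairs are 19.4 (yes, yes), 19.0 (yes, no), 6.2 (no, yes) and 83.4 (no, no).

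- Unpaired chi-square: 0.10² / (0.25 × 0.75 × 2/128) = 3.41, below the critical value of 3.84.
- McNemar: (19.0 − 6.2)² / (19.0 + 6.2) = 6.5, above it.

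Simulated power:

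| phi | ordinary chi-square | McNemar |
|---|---|---|
| 0.1 | 46% | 49% |
| 0.3 | 45% | 60% |
| 0.5 | 44% | 76% |

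**Step 4. Reading 2, no change.** On the time-by-time cross-table the statistic centres near n × phi², whether or not the proportion has moved. At phi 0.3 that is 128 × 0.09 = 11.5, and at phi 0.5 it is 128 × 0.25 = 32, against 3.84. With 30% at both times, simulated rejection is about 92% and about 100%.

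**Step 5. Weekly between-arm tests.** Weeks 5 to 36 make 32 tests per item and weeks 4 to 36 make 33; a start at enrolment fixes no number. At 0.05 each, 32 × 0.05 = 1.6 false-positive weeks are expected per item, whatever the correlation. The chance of at least one is 1 − 0.95³² = 81% if weeks were independent, which answers from the same people are not. With equal correlation of 0.5 to 0.6 between the weekly test statistics (the ICC range borrowed from the primary outcome) it is about 52% to 43%; at 0.8 it is 26%.

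**The case against.** The strongest reply is that McNemar's test is itself a chi-square test and that the plan's wording is permissive, so this may be loose drafting rather than a wrong choice. That is possible. But the same term, equally unqualified, serves for independent arms in the same paragraph, and the continuous counterpart is explicitly paired, so the unpaired reading is the natural one. If McNemar's test was meant, naming it settles the matter.

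Second, the analysis is exploratory, within-arm change is not the randomised comparison, and no primary or Aim 2 result depends on it. All of that stands, and it limits the importance of the point. It does not make a test of association a test of change.

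Third, the size of the loss rests on assumptions. This also stands. Orbit completion is optional, so the number of pairs is unknown. At low correlation the penalty almost disappears, and with the exact form of McNemar's test power at phi 0.5 is 68% rather than 76%. Nor do the documents say which items are categorical: service use and likelihood of placement could be counts or ratings, and the short burden scale and costs look numeric.

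A reader might go further and infer that the plan's stated error rates are wrong, or that the weekly comparisons are invalid. The documents do not support either. No error rate is stated for the Orbit analysis. Each weekly test compares independently randomised people and is valid at its own level; only a family-wise rate is uncontrolled, and none is claimed.

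**Conclusion.** The point holds for the within-group test of categorical items. As written, the rule is either too conservative or answers a different question. On the assumptions above, the first reading costs about 15 percentage points of power at phi 0.3 and 32 at phi 0.5, with little loss at phi 0.1. The second would declare change in nearly every analysis of a stable item once phi is 0.3 or more. The direction of both results does not depend on the assumed prevalence, provided that answers are positively correlated within person; the exact sizes do depend on the assumptions.

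The weekly between-arm testing is a reporting suggestion and not an error. It works in the opposite direction from the conservative reading, since it adds chance findings rather than hiding real ones, and the two should not be merged into one claim about error rates. The consequence is confined to exploratory results.

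**What to change.** In the Orbit paragraph of section 8, replace the sentence on categorical within-group change. Name McNemar's test for binary items and the Stuart-Maxwell test of marginal homogeneity for items with more than two categories. Alternatively, name a GEE or mixed logistic model, which also uses all the weeks and copes better with missed surveys. State which Orbit items are treated as categorical.

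As a secondary suggestion, summarise each item collected in both arms with one repeated-measures model (group, week, group × week), in line with the model already planned for H1 and H2. Keep the weekly values and line charts, and label the weekly p-values descriptive. The number of ABC plans is listed for the ABC group only, so it needs no between-arm model.

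Reconcile the start of the Orbit survey between Measures, Table 2 and Table 3.

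The cost is a few sentences and standard software. No new data are needed, and the paired test has no drawback.

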Video-recordings may be shared with other researchers and those outside of OHSU who are involved in conducting or overseeing research via the secure Webex portal, OneDrive. Using Webex, video streaming links can be sent to identified users via email (which will require a password to access). Study coordinators can download the video files outright from the Webex portal and saved on OHSU's "X" or "H" drives in a highly secure, biometrically authenticated data center or shared via OHSU OneDrive.

Electronic survey data will be stored in a web-accessible server at Qualtrics or REDCap. Copies of this data will be transferred to a secure OHSU server via Application Programming Interface call. Other electronic data will be stored on a secure, password protected OHSU server. Access to data is restricted to study personnel. Access to data requires username/password authentication.

10) Risks and Benefits

a) Risks to Subjects

There are few risks involved in this study. Care Partners will have to meet (via videoconferencing) with the research team and other Care Partners for multiple visits, which may be inconvenient. Care Partners will need to find an activity for their care recipients during the sessions, which may cause financial hardship for some. All visits will be virtual, so there should be no travel costs.

Some of the questions on the scales may seem very personal or embarrassing and fatiguing to participants and may upset them. They may refuse to answer any of the questions that they do not wish to answer. If the questions make them very upset, we will refer them to a social worker.

There is a risk that the video-recordings may be seen by someone they know. It is possible that someone viewing the videos may recognize them, their family members or others and/or hear their names in the audio, and their identities would no longer be confidential. The Care Partners will see each other's' video and audio and share contact information, thus, their identities will not be confidential.

Despite our instruction, care partners will likely text and email us. We cannot control this. We will inform them in consent process of the risks involved.

No part of STELLA-FTD study participation for the Care Partners should result in a serious adverse event as defined by the NIA Adverse Event and Serious Adverse Event Guidelines: ⁽⁶⁶⁾

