Any adverse event that results in death; is life threatening or places the participant at immediate risk of death from the event as it occurred; requires or prolongs hospitalization; causes persistent or significant disability or incapacity; results in congenital anomalies or birth defects; and/or is another condition which investigators just to represent significant hazard.

There may be other adverse events for Care Partners as defined by the NIA Adverse Event and Serious Adverse Event Guidelines⁽⁶⁶⁾

Any untoward or unfavorable medical occurrence in a human study participant, including any abnormal sign (e.g. abnormal physical exam or laboratory finding), symptom, or disease, temporally associated with the participants' involvement in the research, whether or not considered related to participation in the research.

Due to the known strain of caregiving, Care Partners may report mental health issues (e.g., anxiety, depression) or physical manifestations of stress (e.g., hypertension, low back pain). These will likely not be related to the intervention, however, emotional distress is a potential risk of study participation, thus training will be provided to all study team members (including all study investigators, Guides and research assistants) to (a) sensitize them to the signs, symptoms and/or indicators of extreme emotional upset, (b) enable them to make an appropriate immediate response and (c) ensure that project protocol, below, for providing information about resources is carried out appropriately.

Brief Description of the Response Protocol: In the event that any participant displays significant psychological stress as identified by any member of the study team, the Principal Investigator will be notified within 24 hours ([name]) (off hours and on weekends, one of the co-PIs or experienced Guides will be notified). [name] (or her delegate) will reach out to the participant with appropriate resources (hotlines, websites, etc.). To the extent possible, these resources will be local to the participant in question. Resources provided to Care Partners are detailed in section 1.3 "Protection Against Study Risks." [name] (or her delegate) will be responsible for reporting adverse events to SO, NIA, IRB during normal reporting intervals.

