It is possible that the **persons with FTD** who are enrolled in STELLA-FTD may experience a serious adverse event as defined by the NIA Adverse Event and Serious Adverse Event Guidelines. These SAEs would not be a result of the intervention (the persons with FTD do not participate the intervention). Rather, these events will likely be due to advancing FTD and/or health concerns that come with advancing age (e.g., agitation, falls, urinary tract infections, pneumonia) and are expected. It is expected that some participants with FTD will die, and/or be placed in hospice while they are enrolled in the study.

Hospitalizations and deaths in persons with FTD will be considered expected SAEs for the participants with advancing FTD or conditions associated with aging and therefore reported in quarterly reports

We also expect adverse events for the **persons with FTD** as defined by the NIA Adverse Event and Serious Adverse Event Guidelines.⁽⁶⁶⁾ These AEs would not be a result of the intervention (the persons with FTD do not participate the intervention). Rather, these events will likely be due to advancing FTD and/or health concerns that come with advancing age (e.g., agitation, urinary tract infections, pneumonia).

We will report SAEs and AE's per directions laid out by the NIA:

- Only Unexpected SAEs for those who participate in the intervention (i.e., only care partners and not the persons with FTD, who are still considered research participants due to measures being collected about them but do not receive the intervention) will be reportable to the IRB, SO and NIA via expedited reporting (i.e., within 48 hours).
- Expedited reporting to NIA PO, SO and IRB (i.e., within 48 hours of study team's awareness) will only be required for care partners who experience adverse events that are both serious (SAE) and unexpected (i.e., have not been previously reported for the study's intervention).
- The summary of all other SAEs will be reported to NIA Program Officer and to the Safety Officer **quarterly**, unless otherwise requested by the Safety Officer. SAEs for those who do not participate in the intervention (i.e., persons with FTD) will be reportable quarterly (i.e., in quarterly summary reports).
- Hospitalizations and deaths will be considered expected SAEs for the participants with advancing FTD or conditions associated with aging (i.e., PLWD) and therefore reported in quarterly reports.

a. Potential Benefits to Subjects

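### The 48-hour rule treats an SAE as unexpected only if it has not been reported before, so a repeat SAE in care partners moves by default to the quarterly summary

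*Combined protocol and SAP*

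**What the plan says.** The reporting rules are the bulleted list near the end of section 10(a), Risks to Subjects.

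- **Scope.** The fast route covers "Only Unexpected SAEs for those who participate in the intervention", meaning care partners and not the persons with FTD.
- **Timing and recipients.** "Expedited reporting to NIA PO, SO and IRB (i.e., within 48 hours of study team's awareness) will only be required for care partners" whose events are "both serious (SAE) and unexpected (i.e., have not been previously reported for the study's intervention").
- **Everything else.** A quarterly report, which the Safety Officer may ask to have handled differently: "The summary of all other SAEs will be reported to NIA Program Officer and to the Safety Officer".
- **Events named in advance as expected SAEs.** "Hospitalizations and deaths in persons with FTD will be considered expected SAEs". There is no such list for care partners.

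Earlier in the same section, the Response Protocol for distressed participants ends by saying that the Principal Investigator or a delegate "will be responsible for reporting adverse events to SO, NIA, IRB during normal reporting intervals". The list of rules is introduced as following NIA directions, which the document does not reproduce.

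**The concern.** Expectedness is normally judged by comparing an event with what was foreseen before the trial. Here it is judged by whether the event has been reported before, and the parenthesis is worded as a definition, not an example. The first SAE of some kind in a care partner is therefore urgent, and the next similar one is not. Repetition is what helps a Safety Officer tell background illness from a possible effect of participation, so the rule lowers urgency just as the information becomes more useful.

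What is at stake is how soon the bodies outside the study team (NIA, Safety Officer, IRB) see a second or third similar event. Group sessions could continue in the meantime.

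**Working it through.** The plan states no figure for this rule, so there is nothing to reproduce. The check is a reading of the rules against each other, followed by the delay arithmetic.

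**Tracing two similar care-partner SAEs**

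1. The first event is serious, occurs in a care partner and has not been reported before. It meets the definition and goes to the NIA Program Officer, Safety Officer and IRB within 48 hours of the team's awareness.
2. A later, similar event is also serious and also in a care partner, but an event like it has now been reported. On the literal definition it is not unexpected, so the fast route is not required.
3. It then belongs to all other SAEs, which go into the quarterly summary unless the Safety Officer asks otherwise.
4. Nothing elsewhere reverses step 2. There is no list of expected care-partner SAEs, and no rule on number, severity or frequency sends a repeat back to the 48-hour route.

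Step 2 depends on how similarity is judged (diagnosis, organ system, severity), and the text does not say. Nor does it say whether reports from the pilot count as reports for the intervention. If they do, even a first event in this trial could miss the fast route.

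**Delay**

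Inputs: 48 hours and quarterly (section 10(a)); 8-week intervention (section 4). Assumptions: the summary is issued at the end of each quarter without further lag, and events fall evenly over the quarter.

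- Fast route: 48 hours = 2 days.
- Longest default wait: 365.25 / 4 = 91.3 days, which is 91.3 / 2 = about 46 times longer.
- Mean default wait: 91.3 / 2 = 45.7 days.
- The intervention lasts 8 × 7 = 56 days. A repeat in the first 91.3 − 56 = 35.3 days of a quarter (35.3 / 91.3 = 39% of repeats) would wait longer than a full course of sessions.

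**Number of events**

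The documents give no SAE rate for care partners. The following is illustration only, at an assumed 2% to 10% per year:

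- 300 care partners followed for 36 weeks: 300 × 36 / 52.18 = 207 person-years, or 4.1 to 20.7 SAEs of all kinds.
- If the 15% withdrawal allowed for in section 4 all happened at the start: 255 × 36 / 52.18 = 176 person-years, or 3.5 to 17.6 SAEs.

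How many of these would be repeats depends on the undefined matching rule. No count is claimed.

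**The case against.** The strongest reply is the override. The quarterly sentence lets the Safety Officer request something different, and the Safety Officer will have seen the first event within 48 hours. A reader might infer that a cluster will necessarily be seen late; the text does not support that. What stands is that the override is discretionary, has no trigger, and has to be used before the repeats are visible to the person who would use it. The study team itself knows of each event as it becomes aware of it. The delay concerns external oversight only.

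Three other stronger readings are tempting and should not be made.

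- **A contradiction with the risk statement.** Section 10(a) also says "No part of STELLA-FTD study participation for the Care Partners should result in a serious adverse event". That is a statement about causation. It does not say that no care partner will have an SAE, or which SAEs count as expected for reporting. The two statements are compatible.
- **A competing route in the Response Protocol.** Its closing sentence speaks of adverse events in general, and the later list gives the specific rule for unexpected SAEs. The specific rule naturally governs, so a cross-reference would be a convenience.
- **Exclusion of the IRB.** The quarterly sentence does not name the IRB, but the Response Protocol includes it at normal reporting intervals. The two sentences are inconsistent on recipients; they do not show that the IRB is left out.

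It is also fair to say that the study is submitted on a minimal-risk template, that care-partner SAEs may be few, and that the list is said to follow NIA directions. The first two limit the practical impact. The third means that new wording needs the NIA's agreement. None of them changes what the definition does when applied as written.

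**Conclusion.** The point holds as a defect in a definition. Under the current wording, a care-partner SAE similar to one already reported leaves the 48-hour route by default. It reaches the NIA Program Officer and Safety Officer in up to about 91 days, with a mean of about 46, instead of 2. This rests on reading the parenthesis literally, on some notion of similarity that the text leaves open, and on summaries issued promptly at quarter end with events spread evenly.

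Late external sight of repeats is the default and can be overridden. How many events would be affected is unknown. This is a low-cost improvement to safety oversight and does not touch the sample size, the analysis or the intervention.

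**What to change.** In the expedited-reporting bullet of section 10(a), replace the parenthesis with a definition along these lines:

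> *A care-partner SAE is unexpected if its nature, severity or frequency is not consistent with the risks and expected events listed in this protocol. An earlier report of a similar event in this trial does not by itself make it expected.*

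The section already describes mental-health and stress-related complaints that care partners may report, so there is something to compare against. A blanket statement that no care-partner SAE is ever expected would go further than the defect needs.

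In the quarterly bullet, name the recipients consistently with the Response Protocol, so that it is clear whether the IRB receives the periodic summary. An exception in the Response Protocol's last sentence for SAEs that meet the expedited rule is an optional clarification.

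Confirm the wording with the NIA before amending. The cost is a short protocol amendment, that confirmation, and some additional 48-hour reports. Their number cannot be predicted from the documents, but it cannot exceed the number of care-partner SAEs.
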